4.2. Exclusion Criteria

1. Female who is lactating
2. Female who is pregnant according to the pregnancy test at Screening or prior to the first study drug administration
3. Female using the following systemic contraceptives: oral, patch or vaginal ring, in the 28 days prior to the first study drug administration and during the study
4. Female using hormone replacement therapy in the 28 days prior to the first study drug administration and during the study
5. Female using the following systemic contraceptives: injections or implant, or hormone releasing intrauterine device in the 13 weeks prior to the first study drug administration and during the study
6. Drinking excessive amounts of tea, coffee, chocolate, and/or beverage or eating food containing caffeine (> 2 cups/day)
7. Use of tobacco or nicotine containing products (including but not limited to; cigarettes, electronic cigarettes, pipes, cigars, chewing tobacco, nicotine patch, or nicotine gum) within 90 days prior to the first study drug administration and the inability to abstain from nicotine containing products until the follow-up visit.
8. Past or current history of any mental, behavioral, or neurodevelopmental disorder as defined by the Diagnostic and Statistical Manual of Mental Disorders, Fifth Edition (DSM-5) or significant risk of developing a psychosis (assessed by PRIME screen) or a personal history of psychotic symptoms (hallucinations or delusions) with or without a formal psychiatric diagnosis. Subjects with family history of significant mental, behavioral, or neurodevelopmental disorders unless determined by the Investigator (or designee) and agreed by the Medical Monitor to be non-clinically significant (NCS) will be excluded.

9. History or clinical manifestation of any metabolic, allergic, dermatological, hepatic, renal, hematological, pulmonary, gastrointestinal, neurological, respiratory, or endocrine disorder, unless determined by the Investigator (or designee) and agreed by the Medical Monitor to be NCS
10. Active or history of cardiovascular or cerebrovascular disease, including hypertension, angina, ischemic heart disease, transient ischemic attacks, bundle branch block, evidence of myocardial ischemia, stroke, and peripheral arterial disease sufficient to cause symptoms and/or require therapy to maintain stable status
11. History of significant hypersensitivity, intolerance, or allergy to any drug compound, food, or other substance, unless approved by the Investigator (or designee)
12. Active neoplastic disease or history of any neoplastic disease within 5 years of Screening (except for basal or squamous cell carcinoma of the skin or carcinoma in situ that has been definitely treated with standard of care)
13. Active infection (eg, sepsis, pneumonia, abscess) or a serious infection (eg, resulting in hospitalization or requiring parenteral antibiotic treatment) within 6 weeks prior to dosing
14. History of stomach or intestinal surgery or resection that would potentially alter absorption and/or excretion of orally administered drugs (uncomplicated appendectomy and hernia repair will be allowed)
15. Any of the following at Screening and/or prior to the first study drug administration:
 - a. QT interval corrected for heart rate using Fridericia's method (QTcF) > 450 ms confirmed by repeat measurement
 - b. QRS duration > 110 ms confirmed by confirmed by repeat measurement
 - c. PR interval > 220 ms confirmed by repeat measurement
 - d. Findings which would make QTc measurements difficult or QTc data uninterpretable
 - e. History of additional risk factors for torsades de pointe (eg, heart failure, hypokalemia, family history of long QT syndrome)
16. Maintenance therapy with any drug or significant history of drug dependency or alcohol abuse (> 3 units of alcohol per day, intake of excessive alcohol, acute or chronic)
17. Positive test result for alcohol, cotinine, and/or drugs of abuse at Screening or prior to the first drug administration
18. Positive screening results to HIV Ag/Ab combo, hepatitis B surface antigen or hepatitis C virus tests
19. Any other clinically significant abnormalities in laboratory test results at Screening that would, in the opinion of an Investigator, increase the subject's risk of participation, jeopardize complete participation in the study, or compromise interpretation of study data
20. Intake of an IP in the 28 days prior to the first study drug administration
21. Use of any prescription drugs in the 28 days prior to the first study drug administration, that in the opinion of an Investigator would put into question the status of the participant as healthy

22. Use of St. John's wort in the 28 days prior to the first study drug administration and during the study
23. Consumption of any foods or beverages which alter CYP1A2 activity, e.g., barbecued food or cruciferous vegetables, such as broccoli and cauliflower, within 14 days prior to (first) check-in (a list of prohibited foods will be provided to subjects)
24. Consumption of any foods or beverages containing Seville-type oranges, grapefruit, or poppy seeds within 7 days prior to (first) check-in
25. Receipt of blood products within 2 months prior to check-in
26. Donation of 1 unit of blood to American Red Cross or equivalent organization or donation of over 500 mL of blood in the 56 days prior to the first study drug administration
27. Donation of plasma in the 7 days prior to the first study drug administration
28. Poor peripheral venous access
29. History or significant hypersensitivity to TMP301 or any related products (including excipients of the formulations) as well as severe hypersensitivity reactions (like angioedema) to any drugs
30. Subjects who, in the opinion of the Investigator (or designee; including input from subjects' general practitioner, as applicable), should not participate in this study
31. Subject hospitalized for any reason in a period of 30 days before the start of the study
32. Subjects who are investigational site staff members or directly involved in the conduct of the study and their family members or subjects who are employed by the Sponsor

4.3. Withdrawal Criteria

4.3.1. Before First Treatment Administration

Before the first treatment administration, inclusion/exclusion criteria will govern the subjects to be dosed. Subjects withdrawn before first treatment administration will not be followed up and will not undergo End-of-Study/Early Termination assessments. Other safety assessments may be performed if required.

Subjects are free to withdraw their consent to participate in the study at any time, without prejudice. The reason for their withdrawal or for deciding to end their participation will be documented.

4.3.2. After First Treatment Administration

Subjects may, at any time, voluntarily withdraw from the study or be removed from the study at the discretion of an Investigator or Sponsor. If such withdrawal occurs, or if the subject fails to return for visits, an Investigator should determine the primary reason for a subject's premature withdrawal from the study and record the reason in the subject's study documents.

If a subject is withdrawn, the Sponsor will be notified and the date and reason(s) for the withdrawal will be documented in the subject's electronic Case Report Form (eCRF). If a subject

is withdrawn, the Investigator should make every effort to perform a final study visit 7 days after the last administration of the investigational product (IP) and complete the assessments and procedure outlined in the SOA. Other procedures may be performed at the Investigator's (or designee's) and/or Sponsor's discretion. If the subject is in-house, these procedures should be performed before the subject is discharged from the clinic, where possible. The Investigator (or designee) may also request that the subject return for an additional follow-up visit. All withdrawn subjects will be followed until resolution of all their AEs or until the unresolved AEs are judged by the Investigator (or designee) to have stabilized.

Subjects who are withdrawn for reasons not related to the study drug may be replaced following discussion between the Investigator and the Sponsor. Subjects withdrawn as a result of AEs thought to be related to the study drug will not be replaced.

In the case of a clinically significant illness detected during the trial (including Coronavirus Disease 2019 [COVID]-19 diagnosis), the Principal Investigator (or delegate) will, in concert with the Sponsor, determine the most appropriate course of action on an individual basis.

Evaluations will include but are not limited to:

- The safety of the subject and other study participants
- The possible effect the illness would have on the results gathered during the trial, and their ability to be appropriately analyzed or interpreted
- The possibility of suspending participation then re-initiating it after recovery
- The implication of any inclusion or exclusion criteria that would contradict possible actions
- The implication of any adherence to regulatory guidelines that may be affected by actions decided, for example group effect analysis
- The sample size calculation, current number of subjects, and possibility of replacement subjects

Evaluations and decision-making for subject removal will be documented in the study file, reported to the Sponsor, reviewed during cohort safety evaluation and discussed where appropriate in the Clinical Study Report (CSR).

4.3.2.1. Stopping Rules

4.3.2.1.1. Individual Subject Stopping Rules

A subject will be withdrawn, and study treatment discontinued, if any of the following criteria are met:

- Change in compliance with any inclusion/exclusion criterion that is clinically relevant and affects subject safety as determined by the Investigator (or designee).
Any clinically relevant sign, symptom, or intercurrent illness that, in the opinion of the Investigator (or designee), warrants subject withdrawal.

- Non-compliance with the study restrictions or other unanticipated logistical event that might affect subject safety or study assessments/objectives, or as considered applicable by the Investigator (or designee).
- Occurrence of a serious adverse event associated with active IP administration.
- A subject experiences increased ALT or AST $\geq 3 \times$ ULN.
- A subject has a creatinine $> 1.2 \times$ ULN or an increase in serum creatinine by $\geq 30 \mu\text{mol/L}$ (or 0.34 mg/dL) within 24 hours or an increase in serum creatinine to $\geq 1.5 \times$ baseline within 7 days.
- A subject has an increase of > 60 msec from baseline (predose on Day 1 of each treatment period, as applicable) in QTcF.
- A subject with any QTcF > 500 msec confirmed by the average of 2 additional ECG recordings performed at least 5 minutes apart, or other clinically significant conduction disturbance or arrhythmia.
- A subject has a heart rate < 45 bpm or heart rate > 130 bpm, confirmed by a repeat assessment
- A subject has a systolic blood pressure < 80 or > 155 mmHg, or a diastolic blood pressure > 100 mmHg, confirmed by a repeat assessment

In the event of a subject meeting any of the above withdrawal criteria, the Sponsor's Medical Monitor may deem it necessary for unblinding to occur.

4.3.2.2. Trial Stopping Rules

During active dosing of a cohort, the Investigator must contact the Sponsor immediately to discuss whether to suspend dosing if an AE or laboratory abnormalities indicate that continued dosing of subsequent subjects would not be tolerated or would jeopardize the subjects' safety. The Sponsor alone may suspend dosing at any time for any reason.

Active dosing of all subjects within a cohort must be stopped with any of the following:

- If 1 SAE occurs in a subject receiving active IP
- If 'severe' non-serious adverse reactions (ie, severe non-serious adverse events considered as, at least, possibly related to TMP-301) in 2 subjects in the same cohort, independent of within or not within the same system-organ-class.
- One or more subjects fulfill Hy's law defined as increases in aspartate aminotransferase (AST) or alanine aminotransferase (ALT) $\geq 3 \times$ upper limit of normal (ULN) and total bilirubin $\geq 2 \times$ ULN (confirmed with repeat testing) where no other reason can be found to explain the combination of increases, e.g., elevated serum alkaline phosphatase (ALP) indicating cholestasis, viral hepatitis, or administration of another drug.
- Occurrence of 1 death attributable to the study treatment

If any of the above scenarios occur, all active dosing will stop, and no new cohorts will be initiated. Further discussion will then occur within the SRC, and a safety review will be

conducted. Following the SRC review, the study may continue if the Investigator and Sponsor agree it is safe to proceed. If the study is stopped, the MTD will be declared at the next lowest dose that was found to be safe and tolerable.

Following completion of a dosing cohort, a safety evaluation will take place to determine if it is safe to dose escalate in a subsequent cohort. If any of the following occur, no subsequent dose escalation will occur:

- ≥ 2 subjects within the same cohort meet the same individual subject stopping rule at least possibly related to study treatment (see section 4.3.2.1.1).
- ≥ 2 subjects within the same cohort experience any severe AEs at least possibly related to study treatment.
- ≥ 2 subjects within the same cohort experience clinically significant laboratory abnormalities of the same character at least possibly related to study treatment.
- ≥ 1 subjects with a serious adverse event considered at least possibly related to study treatment.

If cohort dose escalation is stopped, the MTD will be declared as the next lowest dose that was found to be safe and tolerable.

4.4. Lifestyle and/or Dietary Requirements

- Subjects will be prohibited from consuming food or beverages containing Seville-type oranges, grapefruit, or poppy seeds within 7 days prior to (first) check-in and during the study.
- Subjects will eat only the food provided by the study site during confinement at the CRU.
- Subjects will not be permitted to use tobacco or nicotine containing products (including but not limited to; cigarettes, electronic cigarettes, pipes, cigars, chewing tobacco, nicotine patch, or nicotine gum) within 90 days prior to the first study drug administration and must be willing to abstain from nicotine containing products until the follow-up visit.
- Subjects will be prohibited from consuming alcohol for 48 hours prior to dosing and throughout the study. Throughout the study, in case of any doubt about alcohol consumption, a test for alcohol may be performed if requested by an Investigator.
- Subjects will be prohibited from consuming any foods or beverages which alter CYP1A2 activity (e.g., barbecued food or cruciferous vegetables, such as broccoli and cauliflower) for 14 days prior to check-in and through the end of the study (a list of prohibited foods will be provided to subjects).
- Subjects must abstain from caffeine for 48 hours prior to check-in and will be prohibited from drinking coffee or caffeine containing beverages throughout the study, except when caffeine is being administered as part of the study procedures.

- Males who are sexually active will be made aware of the possible male-mediated fetal toxicity associated with the study drug. Male subjects will be expected to use an acceptable contraceptive regimen and not to donate sperm as described in Section 4.1.

4.5. Concomitant Treatment

In addition to the drugs prohibited as per the exclusion criteria (Section 4.2), subjects will also be prohibited from taking any over the counter (OTC) products for 14 days prior to the first dosing and for the entire duration of the study.

Medications that are substrates, inhibitors, or inducers of CYP1A2 are specifically prohibited (including, but not limited to, those containing caffeine (except where part of the study design), tizanidine, theophylline, naproxen, fluvoxamine, cimetidine, fluoroquinolones, or ticlopidine).

Occasional use of paracetamol/acetaminophen at doses \leq 2 grams/day will be permitted at the Investigator's discretion.

Except for medication which may be required to treat AEs, no other treatment, medication, or dietary supplement (including herbal/vitamin supplements) other than the study drugs will be allowed from the first dosing until all study activities and evaluations have been completed.

Subjects will be instructed to notify the study site about any new medications taken after the start of the study treatment. All medications and significant non-drug therapies (including physical therapy and blood transfusions) administered after the subject has received the study treatment must be listed in the subject case report form (CRF). The drug name and dose taken will be noted. An Investigator or delegate and/or the Sponsor will decide whether the subject will be permitted to remain in the study, depending on the drug used, the time of drug intake, etc.

5. STUDY TREATMENTS

5.1. Investigational Products

All IPs, including the placebo, will be provided by the Sponsor.

5.1.1. TMP-301

5.1.2. Placebo

Commercially Confidential Information

5.2. Investigational Product Management

5.2.1. Packaging, Labeling and Dispensing

Commercially Confidential Information

5.2.2. Storage and Handling

All study drugs will be shipped from the sponsor or sponsor resources to the CRU's pharmacy.

TMP-301 should be stored between 2°C and 8°C and kept in a tightly closed container. The product should not be used if expired and should not be frozen.

The CRU's pharmacy will maintain an inventory record of the IPs received, stored (in a secure restricted area), and dispensed. IPs will be provided to study subjects only.

5.2.3. Method of Assigning Subjects to Treatment Groups

Altasciences will generate the randomization code with a computer program according to the study design, the number of subjects and the number of treatments. Within each cohort, subjects will be randomized (3:1) to receive TMP-301 or placebo. The random allocation of each IP to each subject will be done in such a way that the study is balanced. Once generated, the randomization code will be final and will not be modified.

Subjects who sign the ICF and are randomized but do not receive the study treatment may be replaced. Subjects who sign the ICF, are randomized and receive the study treatment, and subsequently withdrawn as a result of AEs thought to be related to the study drug will not be replaced. Subjects who sign the ICF, are randomized and receive the study treatment, and are subsequently withdrawn for reasons not related to the study drug may be replaced.

5.2.4. Blinding

The randomization code may be made available to the personnel of the bioanalytical facility. The treatment assignment will not be known by the study participants.

Furthermore, the randomization code will not be available to the physician and clinical staff involved in the collection, monitoring, revision, or evaluation of AEs, as well as clinical staff who could have an impact on the outcome of the study, and including the pharmacokineticist (or delegate), until database lock, or designation that unblinding information is required by the SRC to determine the next dose.

The preparation of the products will be done by designated personnel that are not directly involved in the clinical aspects of the trial.

The randomization code must not be broken except in emergency situations where the identification of a subject's study treatment is required by an Investigator for further treatment to the subject or to complete a SAE report. Randomization information will be held by designated individual(s). The date and reason for breaking the blind must be recorded.

The results of the PK analyses will be made available only to the personnel responsible for evaluating the safety data before proceeding with the next dose level.

5.2.5. Study Drug Accountability

Complete and accurate inventory records of all study drugs will be maintained. This includes acknowledgment of receipt of each shipment of study product (quantity and condition), subject dispensing records, and returned or destroyed study product.

At the conclusion of the study, all unused IPs and all medication containers will be returned to the Sponsor unless the Sponsor has approved other arrangements. Drug accountability will be performed at the completion of the trial.

5.3. Administration of Study Drug

For cohort 1, the study drug will be administered twice daily (12 hours apart) on Days 1-13 and once in the morning on Day 14. For cohort 2 (and Cohorts 3-4 if done) the study drug will be administered once daily in the morning on Days 1-14. The date and time of each dose will be recorded. For each subject, all scheduled post dose activities and assessments will be performed relative to the time of the first study drug administration.

Commercially Confidential Information

On Day -1, caffeine will be administered at approximately 9:00 am with approximately 240 mL of water at ambient temperature test. On Day 14, caffeine will be administered with the study drug and approximately 240 mL of water.

5.3.1. Treatment Compliance

The study drug will be dispensed only to eligible subjects and administered under the supervision of study personnel. Treatment compliance will be verified according to the site's standard operating procedures (SOPs).

5.4. Meals

Food intake will be controlled for each confinement period and for all subjects.

Subjects will be required to fast overnight for 10 hours prior to the morning dose and for at least 2 hours following dosing. Subjects will also be required to fast for 2 hours prior to the evening dose and 2 hours following dosing for bid dosing.

For cohort 3 and 4, dosing may be conducted in the fed state (see section 3.1). In that case, subjects will be required to fast overnight for approximately 9 hours. Each subject will be served

a standard breakfast, and the study treatment will be administered 30 minutes after initiation of the meal.

Fluid intake other than water will be controlled for each confinement period and for all subjects. Each dose of TMP-301 will be administered with approximately 8 oz or 240 mL of water. Water will be permitted as needed except from 1-hour predose until 1 hour after dosing (except for water consumed for the dose administration). For cohort 3 and 4, if dosing is conducted in the fed state, there will be no water restriction during the meal.

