3. STUDY DESIGN

3.1. Adaptive Features and Risk Management of Study Design

The rationale of having the following adaptive features is based on the hypothesis-forming approach of this clinical trial. Dose escalation or de-escalation, including titration, categories will be adapted as follows:

Table 1: Adaptive Features and Boundaries

| Adaptive study design category | Adaptive Features | Boundaries |
|--------------------------------|--|---|
| Dose adjustment | Doses for the subsequent cohorts will be determined/adapted based on tolerability, and PK data (if data through Day 15 permits and is available) collected in previous cohort. | Doses are intended to escalate; however, they may be adjusted to a lower, an equivalent dose or a higher dose as per the adaptive features. For any cohort the mean maximum systemic exposure should not exceed or be predicted to exceed an AUC_{0-24} of 16,200 $h.ng/mL$ at steady state and/or a maximum serum concentration predicted to exceed a C_{max} of 783 ng/mL^a |
| The number of MAD cohorts | The quantity of MAD cohorts may be adapted | The maximal number of different dose level cohorts will be 4. |
| Dose Titration | Dose titration may be added in this study based on interim safety data reviews and tolerability to the study drug. | Based on safety/tolerability findings in any of the previous cohorts, a 14 day dose titration cohort (7 days at initial dose + 7 days at higher dose) may be added. |
| Dosing with meals | Dosing may be done in a fasted or fed state. | At the selected dose level, the predicted effect of food on exposure will not exceed the thresholds described above. |

Abbreviations: MAD = multiple ascending dose; PK = Pharmacokinetics.

^aExposure limits were based on 28D Rat NOAEL exposures, with an additional 10x safety factor.

Commercially Confidential Information

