3.3. Overall Study Design

This study will be a randomized, double-blind, placebo controlled, fixed sequence, MAD study. The study will be conducted in a single clinical research unit (CRU). The study will consist of up to 4 cohorts. Each cohort will consist of 8 subjects (6:2 for active: placebo), for a maximum total sample size of approximately 32 subjects. Subjects will only participate in 1 cohort.

Screening will occur within approximately 28 days prior to the first scheduled study drug administration. Screening data will be reviewed to determine subject eligibility. Subjects who meet all inclusion criteria and none of the exclusion criteria and who consent to participation will be admitted to the CRU for baseline evaluations prior to dosing. All baseline safety results should be available prior to the first study drug administration.

In cohort 2, subjects will be fasted overnight for 10 hours prior to the morning dose, followed by a 2 hour fast. Subjects were fasted for 2 hours prior to dosing and 2 hours following the evening dose for the cohort 1 (50 mg bid). If dosing in a fed condition is selected for cohort 3 or 4 (see section 3.1), subjects will be fasted overnight for approximately 9 hours, then given standard breakfast followed by study treatment dosing 30 minutes after initiation of breakfast.

Each subject will be randomly assigned to 1 of the following cohorts:

- Cohort 1: Group 1 (6 subjects): 50 mg of TMP-301 bid
Group 2 (2 subjects): placebo (matching TMP-301) bid
- Cohort 2: Group 3 (6 subjects): 50 mg of TMP-301 qd
Group 4 (2 subjects): placebo (matching TMP-301) qd
- Cohort 3: Group 5 (6 subjects): Dose regimen of TMP-301 to be determined
Group 6 (2 subjects): placebo (matching TMP-301)
- Cohort 4: Group 7 (6 subjects): Dose regimen of TMP-301 to be determined
Group 8 (2 subjects): placebo (matching TMP-301)

Safety will be assessed and blood samples for PK will be collected throughout confinement. Subjects will be discharged from the CRU on Day 18. Subjects will return to the CRU on Day 25 for a follow-up visit and EOS procedures.

Caffeine (100 mg) will be included as probe CYP1A2 substrate in cohort 2 and subsequent cohorts. Ratio of plasma paraxanthine/caffeine will be determined in a blood sample 4 hours after administration of caffeine at baseline (Day-1) and on day 14.

The maximum duration of subject participation, including Screening, will be approximately 53 days.

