10.6.2 Dose Proportionality

Natural log-transformed PK parameters ($C_{\text{max, ss}}$, $C_{12, \text{ss}}$, $C_{24, \text{ss}}$, and $AUC_{0-\text{TAU, ss}}$) will be assessed statistically for proportionality. Proportionality analysis will be done using a power model. The power model is defined as:

$$\ln(\text{PK parameter}) = \alpha + \beta \cdot \ln(\text{Dose}) + \varepsilon$$

where α is the intercept, β is the slope and ε is the error term. A linear model with ln-transformed dose as a continuous effect will be fitted. A point estimate and a 90% confidence interval will be derived for the slope (β).

The parameter can be considered to be dose-proportional if the 90% CIs for the slope coefficient that include 1 will suggest evidence of dose proportionality.

Dose proportionality may be assessed within different dose ranges if deemed appropriate with at least three doses.

Otherwise, if there are only two cohorts completed, Statistical inference will be based on a bioequivalence approach for a parallel group design and expressing the relative difference as a geometric mean ratio and 90% CI using ANOVA model based on dose normalized PK parameters.

No comparison between fed and fast state will be provided.

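### If cohort 3 or 4 is dosed fed at a new dose, the SAP power model would read a food effect as slope; the Day -1 caffeine meal state is also not stated

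*Protocol*

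**What the plan says.** **Food state and dose.** Protocol 3.3 fasts cohort 2: "In cohort 2, subjects will be fasted overnight for 10 hours prior to the morning dose, followed by a 2 hour fast". SAP 6.1 labels both 50 mg groups as fasted. For cohorts 3 and 4, Protocol 5.4 leaves the choice open: "For cohort 3 and 4, dosing may be conducted in the fed state (see section 3.1"). In a fed cohort, "the study treatment will be administered 30 minutes after initiation of the meal". The doses of these cohorts are still to be determined. Protocol Table 1 (section 3.1) says: "Doses are intended to escalate; however, they may be adjusted to a lower, an equivalent dose or a higher dose". Its only condition on the food choice is an exposure ceiling: "At the selected dose level, the predicted effect of food on exposure will not exceed the thresholds described above".

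**Proportionality model.** SAP 10.6.2 regresses the log PK parameter on ln(Dose), reports a 90% CI for the slope, and takes an interval containing 1 as evidence of proportionality. There is no food term. The optional sub-analysis is by dose range, with at least three doses. The section ends: "No comparison between fed and fast state will be provided". SAP 10.6.1 says the same.

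**Caffeine probe (cohort 2 onwards).** Protocol 5.3: "On Day -1, caffeine will be administered at approximately 9:00 am", with water; no meal condition is given in the visible text. Then: "On Day 14, caffeine will be administered with the study drug and approximately 240 mL of water". The endpoint divides the Day 14 paraxanthine/caffeine ratio by the Day -1 ratio, each from one 4 h sample.

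**The concern.** If the fed option is used together with a change of dose, every fed subject has a different dose from the fasted 50 mg subjects. A regression on ln(Dose) alone cannot tell a food effect from a departure from proportionality. A proportional drug could be reported as non-proportional, or a non-proportional one as proportional. These results would inform later dose choices.

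The caffeine ratio has a similar weakness within subject. A paraxanthine/caffeine ratio at a single early time depends on when caffeine was absorbed as well as on how fast it is metabolised. If the meal condition differs between Day -1 and Day 14, a change in absorption could be taken for an effect of TMP-301 on CYP1A2.

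**Working it through.** The plan gives no slope, food effect or variability to reproduce. Food effects, doses above 50 mg, between-subject CVs and caffeine kinetics below are assumptions for illustration, not proposals.

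**1. Slope bias**

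From the documents: 6 active subjects per cohort; cohorts 1 and 2 both 50 mg and fasted, so 12 active at 50 mg. Protocol Table 2 shows fed wording in the row that begins at cohort 2; I follow Protocol 3.3 and the SAP label.

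Assumed: 100 and 150 mg with 6 active each, true slope 1, fed/fasted exposure ratio F.

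Formula: expected slope = 1 + ln(F) × S(dose, fed) / S(dose, dose), with the S terms being centred sums over subjects.

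With ln(dose/50) = 0, 0.693 and 1.099 for 12, 6 and 6 subjects:
- mean = (6 × 0.693 + 6 × 1.099)/24 = 0.448
- S(dose, dose) = 12 × 0.448² + 6 × 0.245² + 6 × 0.651² = 5.31
- 100 and 150 mg both fed: S(dose, fed) = 6 × 0.245 + 6 × 0.651 = 5.38, multiplier 5.38/5.31 = 1.01
- only 150 mg fed: S(dose, fed) = 6 × 0.651 = 3.90, multiplier 3.90/5.31 = 0.74

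| F | ln F | Shift, both fed | Shift, top dose fed |
|---|---|---|---|
| 0.8 | -0.223 | -0.23 | -0.16 |
| 1.25 | +0.223 | +0.23 | +0.16 |
| 1.5 | +0.405 | +0.41 | +0.30 |

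Using only the once-daily 50 mg cohort (6/6/6, both higher doses fed) gives a multiplier of 0.97, so pooling the two 50 mg regimens does not drive the result.

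**2. Effect on the decision rule**

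Simulation of 20,000 trials per scenario, 6 active per cohort, least squares, 90% t-interval. With no food effect the interval contains 1 in about 90% of trials.

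| Fasted doses; fed doses (multiples of 50 mg) | True slope | F | Mean slope | Interval contains 1 at CV 20/30/50% |
|---|---|---|---|---|
| 1, 1; 2, 3 | 1 | 1.25 | 1.23 | 19/48/72% |
| 1, 1; 2, 3 | 1 | 1.5 | 1.41 | 0/8/39% |
| 1, 1, 2; 3 | 1 | 1.5 | 1.30 | 7/31/61% |
| 1, 1; 2 | 1.5 | 0.7 | 0.98 | 90/90/90% |

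The last row is masking: with no food effect that design's interval would contain 1 in 27% of trials at CV 30%.

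**3. Can a food term repair it?**

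With F = 1.5 and CV 30%:
- One fed cohort at a new dose beside the two fasted 50 mg cohorts: the design matrix is singular, so food and dose cannot be separated.
- Fed at 2x and 3x: the slope returns to 1.00, but mean interval width goes from 0.44 to 1.42.
- Fasted at 1x, 1x and 2x, fed at 3x: slope 1.00, width from 0.46 to 0.72.

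**4. Caffeine**

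One-compartment parent and metabolite model with unchanged clearance. Assumed: half-lives 5 h (caffeine) and 4 h (paraxanthine); fasted Day -1 with absorption rate 4/h and lag 0.1 h. The apparent CYP1A2 ratio is the 4 h ratio under each Day 14 condition divided by the Day -1 value.

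| Day 14 absorption rate | Day 14 lag | Apparent CYP1A2 ratio |
|---|---|---|
| 2/h | 0.1 h (unchanged) | 0.93 |
| 1.5/h | 0.1 h (unchanged) | 0.88 |
| 2/h | 0.25 h | 0.89 |
| 1.5/h | 0.5 h | 0.78 |
| 1.5/h | 1.0 h | 0.65 |

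The lowest value needs 1.0 - 0.1 = 0.9 h of extra lag. With the same meal condition on both days this source of difference is removed.

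**The case against.** **The SAP already declines to compare food states.** "No comparison between fed and fast state will be provided" stands inside the proportionality section and can be taken as intent not to mix them. It bars a food contrast, but it does not say that fed cohorts stay out of the regression. Nor should a reader infer that it drops an analysis that could have rescued the slope: where food and dose are aliased, no fed-versus-fasted comparison separates them.

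**The caffeine tests may in fact be matched.** This stands. A reader might infer from Protocol 5.3 and 5.4 that Day -1 is fasted and Day 14 fed. The visible text leaves the Day -1 meal state unstated; food is controlled during confinement, site procedures apply where the protocol is silent, and part of 5.3 is redacted. The documents also say nothing about food and caffeine absorption, so the size and direction in the working are assumed.

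**There is a placebo control.** Placebo subjects in a fed cohort share the Day 14 meal, but there are 2 per cohort and the SAP plans no active-placebo contrast for this ratio.

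**Displays are stratified by treatment.** SAP 10.6 does this where appropriate, and the existing treatment labels carry food state, so a fed cohort would probably appear separately in plots. That does not alter the regression.

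**It is contingent and exploratory.** True. Cohorts 3 and 4 are optional, fed dosing is optional, and a fed cohort at 50 mg once daily would not tie food to dose.

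**Conclusion.** The concern holds conditionally. If a later cohort is fed at a dose other than 50 mg, applying SAP 10.6.2 as written puts any food effect into the slope. In the 50/100/150 mg illustration with both higher doses fed, the shift is -0.23, +0.23 or +0.41 for food effects of 0.8x, 1.25x or 1.5x, enough to change the proportionality conclusion in many trials. The exposure ceiling in Table 1 allows for a food effect but tells us neither its size nor its direction.

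For caffeine, the supported conclusion is narrower: the Day -1 meal condition is unspecified, and matching is not required. A ratio of 0.93 to 0.65 with unchanged CYP1A2 activity is possible only if Day -1 is fasted and Day 14 absorption is delayed as assumed.

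The primary safety objective and the secondary PK parameters are not affected.

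**What to change.** 1. **SAP 10.6.2.** State that the power model is fitted only across cohorts dosed in the same food state. Where too few dose levels remain, report dose-normalised parameters descriptively by food state and draw no proportionality conclusion across food states. The cost is a few sentences. The downside is real: proportionality may rest on fewer doses or not be concluded. In the 50 fasted, 100 and 150 fed example, one fasted and two fed levels remain, fewer than the three doses the SAP asks for when it looks within a dose range.

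2. **Protocol 5.3 and 5.4.** Reconcile these sections so that, within each cohort, the Day -1 and Day 14 caffeine tests are taken under the same stated meal condition. Alternatively, state in the SAP that CYP1A2_ratio is not interpreted as a drug effect in a cohort where the conditions differ. This costs about a sentence, and subjects are already confined on Day -1. A matched condition has to be settled before a fed cohort's Day -1, since the baseline test cannot be recovered later.
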